3.2 General Key Definitions

The following definitions will be used:

- Date of the First Study Treatment Administration: The date of the first study treatment administration is defined as the earliest date on which a study treatment was administered.
- Date of the Last Study Treatment Administration: The date of the last study treatment administration is defined as the latest known date on which a study treatment was administered.
- Baseline: The Baseline value is value taken on Day 1. If Day 1 value is missing, Baseline is defined as the last available valid, non-missing observation for each patient prior to first study treatment administration on Day 1. Repeat and unscheduled assessments will be included in the derivation of the Baseline values only if Baseline visit value is missing.
- Change from Baseline: The absolute change from Baseline value is defined as the difference between the result collected/derived at a post-baseline visit and the Baseline value.

The change from Baseline value at each post-baseline visit will be calculated for all continuous parameters using the following formula:

$$\text{Change from Baseline Value} = \text{Result at post-baseline visit} - \text{Baseline Value}$$

The change from Baseline value will only be calculated if the specific post-baseline visit result and the Baseline value for the parameter are both available and will be treated as missing otherwise. In the data listings, the change values will be set to '-' (not applicable) for pre-baseline assessments.

The rate of change from baseline is defined as: Change from Baseline value/Baseline Value

- Study Day: The study day of an event is defined as the relative day of the event starting with the date of the first study treatment administration (reference date) as Day 1 (there will be no Day 0).

The study day of events occurring before the first study treatment administration will be calculated as:

$$\text{Study Day} = (\text{Date of Event} - \text{Date of First Study Treatment Administration})$$

For events occurring on or after Day 1, study day will be calculated as:

$$\text{Study Day} = (\text{Date of Event} - \text{Date of First Study Treatment Administration}) + 1$$

Study days will only be calculated for events with complete dates and will be undefined for events that are 'Ongoing' at the end of the study.

3.3 Handling of Missing Data

All data will be analysed as collected and missing values will not be imputed or replaced unless stated otherwise.

3.4 Treatment Groups

- Arm A: Ifenprodil (20 mg TID)
- Arm B: Ifenprodil (40 mg TID)
- SOC: Standard of Care

4. ANALYSIS POPULATIONS (*ANALYSIS SETS*)

In this study three analysis populations are defined: The Intent-to-Treat (ITT), Per Protocol (PP) and the Safety population.

4.1 Population Descriptions

4.1.1 ITT

The ITT population consists of all enrolled patients assigned to receive treatment regardless of whether they took study drug or stopped active treatment to receive only SOC. Patients will be classified according to the treatment group to which they were randomized.

4.1.2 PP

The PP population consists of all ITT patients who are not major protocol violators with regards to inclusion/exclusion criteria, investigational product compliance and concomitant medication instructions. Protocol violations that would exclude patients from the PP population will be defined and documented in the SAP prior to unblinding.

4.1.3 Safety

The Safety population consists of all patients who received at least one dose of study drug. This population will be used for all assessments of safety and tolerability. Patients will be summarized according to actual dose of study drug taken.

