### 6.3 Packaging and Labelling

The contents of the label will be in accordance with all applicable regulatory requirements.

**Description of Product:** White, round, biconvex, film-coated tablets containing 20 mg of the active ingredient.

**Investigational Drug Packaging and Labeling:** The study drug (Ifenprodil) will be supplied by Algernon Pharmaceuticals, in cartons containing blister packs (50 tablets contained in 5 blister packs (10 tablets per blister pack)).

The study drug will be provided to the sites by Algernon Pharmaceuticals. Separate labels, as per the GMP regulations and requirements will also be provided for site staff to apply to the packages and blister packs, as provided by the local laws. All investigational labels for the study drug will meet applicable country specific regulatory requirements.

**Storage:** Store in a dry dark place at temperatures no higher than 25°C, keep protected from moisture.

**Dispensing:** Study treatment must be stored in a secure area under the appropriate physical conditions for the product. Access to and administration of the study treatment will be limited to the investigator and authorized site staff.

**Drug Return/Destruction:** The clinical site, upon confirmation with Sponsor, should follow their local regulations for final disposition of unused study treatment.

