2.2 Objectives

2.2.1 Primary objectives

To investigate the clinical efficacy and safety of NP-120 (20 and 40 mg TID) compared to standard of care in patients hospitalized with COVID-19 disease.

- The choice of the primary outcome measure will be determined by a pilot study of the first 150 patients.
- Patient clinical status (on the WHO 7-point ordinal scale) at day 15 is the default primary endpoint

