For SOC, the listing will cover treatment exposure and will be sorted by patient ID and visit for the ITT and Safety population, along with the age, sex, baseline weight of the patient as well as site, ATC Level 2, ATC Level 4 classification of SOC medication/therapy, dosage, unit and route, start and stop dates/ongoing status.

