12. SAFETY

All Safety endpoints will be analysed using the Safety analysis set.

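### The Safety population is defined by a dose of ifenprodil, so read literally it contains no SOC patients; the count table in SAP section 7 also reports ITT and PP membership on that set

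*SAP*

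**What the plan says.** SAP 4.1.3 and Protocol 10.2 set the entry rule: "The Safety population consists of all patients who received at least one dose of study drug". The grouping rule follows: "Patients will be summarized according to actual dose of study drug taken". Protocol 6.3 says what study drug is: "The study drug (Ifenprodil) will be supplied by" the sponsor.

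The objective and the outputs call for a control group. SAP 2.2.1 states the primary aim: "To investigate the clinical efficacy and safety of NP-120 (20 and 40 mg TID) compared to standard of care". SAP 3.4 names three treatment groups, the third being "SOC: Standard of Care". SAP section 12 opens with "All Safety endpoints will be analysed using the Safety analysis set". SAP section 10 states: "For SOC, the listing will cover treatment exposure and will be sorted by patient ID and visit for the ITT and Safety population". SAP 12.2 has a treatment-emergent rule for the SOC arm and tables of SOC-related events for all three arms.

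On membership counts, SAP section 5 bases the summary of analysis populations on all patients. SAP section 7 puts the counts and percentages for ITT, PP and Safety on the Safety population, while its listing is on ITT.

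**The concern.** In Phase 2b the control arm receives neither ifenprodil nor placebo; placebo comes only in Phase 3 (Protocol 4.1). A rule that requires a dose of ifenprodil therefore shuts out the comparator. The grouping rule offers no way back in, because a zero-dose group cannot exist in a set that requires at least one dose.

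Safety against SOC is half of the primary objective, and every safety endpoint uses this set. A programmer who follows the definition gets an empty control column. One who produces the planned three-arm tables has departed from the definition. Neither document says which SOC patients enter or from what date. In an open-label trial, that choice should be fixed in writing before the analysis.

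The section 7 table is a separate fault. It counts a larger population inside a smaller one.

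**Working it through.** **Inputs.** Allocation is 1:1:1 (SAP 2.1). The pilot plans 150 patients, 50 per arm, and 168 enrolled after 10% dropout (SAP 2.5).

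**The plan's own figure.** Per arm, 50 / (1 − 0.10) = 55.6, rounded up to 56; 3 × 56 = 168, which matches. Rounding on the total instead gives 150 / 0.9 = 166.7, or 167, so the plan evidently rounded by arm.

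**Size of the Safety set**, assuming that every patient allocated ifenprodil takes at least one dose and no SOC patient does:

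| | Planned (50 per arm) | Enrolled (56 per arm) |
|---|---|---|
| Literal rule: both ifenprodil arms | 2 × 50 = 100 | 2 × 56 = 112 |
| Literal rule: SOC | 0 | 0 |
| Share of all patients | 100/150 = 66.7% | 112/168 = 66.7% |
| SOC admitted | 150 | 168 |

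**Outputs that rest on the set.** Fourteen SAP sections place an output by treatment arm on Safety. In nine it includes a table: 7, 8.3, 9, 10, 12.2, 12.3, 12.4, 12.5 and 12.8. In five it is a listing only: 5, 6, 11.13, 12.6 and 12.7. Mortality (11.9), the disposition summary (5) and the cytokine summary tables (11.13) use ITT or PP and are untouched.

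**The section 7 count table.** ITT keeps patients "regardless of whether they took study drug or stopped active treatment to receive only SOC". Let u be the number randomized to ifenprodil who never take a dose; the documents give no value. Suppose SOC is admitted to Safety. At 168 enrolled, ITT has 168 members and Safety has 168 − u. A table restricted to Safety can show at most 168 − u ITT patients, so each undosed patient lowers the reported ITT count by one. Safety membership is (168 − u)/(168 − u) = 100% by construction, so the percentage says nothing. Without admitting SOC, the SOC column is 0/0.

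**Reference date.** SAP 3.2 counts study days from first study treatment administration. It does not say which date that is for SOC.

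**Adverse event window.** SAP 12.2 treats all adverse events in the SOC arm as treatment-emergent, and collection starts at consent (Protocol 7.4.12). In the ifenprodil arms the count starts after first dose. Screening may precede randomization by up to 24 hours (Protocol Table 3, note a), and dosing is to begin within 24 hours of screening procedures (Protocol 7.3.1). The planned difference is thus 0 to about 24 hours. Pre-existing conditions found at screening go to medical history (Protocol 7.4.2 and 7.4.7). Expected progression of the disease is not an adverse event unless more severe than expected (Protocol 8.1). Events of unclear timing count as treatment-emergent (SAP 12.2). All three rules narrow the difference. The documents give no event rates, so no size can be put on what remains.

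**The case against.** The strongest reply is that the SAP already settles the intent. SOC is a named group, its exposure listing is on the Safety population, and there are event tables meant for all arms. The zero counts above therefore measure a reading that the SAP's own outputs rule out. The populations must also be approved before the final analysis (SAP 14.2), when an empty control column would be plain to see, and the table shells (SAP section 16) may settle the matter, though they are not available here. This stands as an argument about risk. It does not make the stated rule correct, and it leaves open exactly who enters and from when. SAP 3.2 does use the broader term study treatment, but it does not define it, and 4.1.3 does not use it.

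A second reply is that section 7 does not lose undosed patients, since its listing is on ITT. That is right: the fault is confined to the count table.

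A reader might infer that control patients would actually be dropped, or that no safety comparison with SOC will be made. The documents do not support that; several outputs show the opposite plan. A reader might also infer that the control arm gains a full extra day of adverse event counting and that ifenprodil is materially favoured. That is not supported either: about a day is the upper end of the planned gap, and the recording rules remove much of what could arise in it.

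**Conclusion.** The point holds as a contradiction between a definition and the outputs that depend on it. It should be fixed, although the practical risk is modest because the intent is recoverable. By the stated rule, 0 of 50 planned SOC patients (0 of 56 at full enrolment) belong to the set on which every safety endpoint is analysed. This rests on study drug meaning ifenprodil, as Protocol 6.3 states, and on no SOC patient receiving it.

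The section 7 count table is wrong in its own right, and admitting SOC does not cure it. Its effect equals the number of randomized but undosed ifenprodil patients, which may be zero. The different start of adverse event counting is a minor matter.

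**What to change.** 1. In Protocol 10.2 and SAP 4.1.3, define Safety as all randomized SOC patients plus all ifenprodil-arm patients with at least one dose, summarized as SOC, 20 mg TID or 40 mg TID by treatment actually received. Say expressly that ifenprodil-arm patients who take no dose are outside the set, so that nobody moves them into the SOC group.
2. In SAP section 7, tabulate membership of ITT, PP and Safety on all randomized patients, which removes the conflict with section 5. The listing can stay as it is.
3. In SAP 3.2, state that Day 1 for SOC patients is the date of randomization.
4. Optional: in SAP 12.2, start the SOC count of treatment-emergent events at randomization, using date and time where available. Note that a short interval between randomization and first dose would still count for SOC alone.

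The cost is a few sentences in SAP 3.2, 4.1.3 and 7, one in Protocol 10.2, and one in SAP 12.2 if the optional change is made. No new data are needed: adverse events are already collected from consent, and the randomization date is already part of the disposition listing (SAP section 5).

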5. PARTICIPANT DISPOSITION

Participant disposition and analysis population analysis will be based on the all patient population. Participant disposition and analysis populations will be summarized descriptively as described in 3.1.

The following participant enrolment and disposition information will be reported:

Summary of Enrolment:

- Number of Patients Enrolled
- Number of Patients Re-screened
- Number of Screen Failures
- Reasons for Screen Failure (percentage denominator based on number of screen failures):
 - Failed I/E criteria

Summary of Disposition:

- Number of Patients Completed
- Number of Patients Withdrawn/Not Completed
- Reason for Withdrawal/Non-Completion (percentage denominator based on number of withdrawn patients)

Counts and percentages will be reported for summary of enrolment, for all enrolled patients who gave consent. For the summary of disposition counts and percentages will be provided for the ITT population for treatment groups defined in [section 3.4](#).

Listings will be provided for summary of enrolment along with the date the participant provided informed consent, date received study drug/treatment received and sorted by patient ID . For summary of disposition, listing will be provided by treatment arm ([section 3.4](#)) sorted by patient ID for the Safety population, along with the date of randomization, date and time of first study drug administration, date of treatment termination/last visit.

6. PROTOCOL DEVIATIONS

All protocol deviations and important protocol deviations leading to exclusion from PPS will be categorized as per protocol deviation management plan version 1.0, 14 July 2020.

Listing of protocol deviation including information on whether the protocol deviation lead to exclusion from PPS will be provided by treatment arm ([section 3.4](#)) sorted by patient ID for the Safety population. Age and sex of the patient, date and time of first study drug administration, date of treatment termination/last visit, and whether the patient completed the study will also be included in the listing.

7. ANALYSIS POPULATIONS

The following analysis set information will be reported:

- Patients included in ITT
- Patients included in PPS
- Patients included in Safety

Counts and percentages for these patients under this population set will be provided using the Safety population for treatment groups defined in [section 3.4](#)

Listing of patients in analysis sets will be provided by treatment arm ([section 3.4](#)) sorted by patient ID for the ITT population, along with date and time of study drug administration, date of treatment termination/last visit, and whether the patient completed the study.

8. DEMOGRAPHICS AND MEDICAL HISTORY

8.1 Demography and Baseline Characteristics

The demographics variables to be reported are listed below:

- Age (years)
- Age classification (< 65 and ≥ 65)
- Gender
- Women of child-bearing potential
- Contraception used – Female
- Contraception used – Male
- Ethnicity
- Race
- Height (cm) at Baseline
- Weight (kg) at Baseline
- BMI (kg/m²) at Baseline
- BMI < 18.5 (Underweight), 18.5 ≤ BMI < 25 (Normal), 25 ≤ BMI < 30 (Overweight) and BMI > 30 (Obese).

These variables will be summarized using descriptive statistics in accordance to [section 3.1](#) under ITT and PPS population for treatment groups defined in [section 3.4](#). Demographics variables and site will also be listed by treatment arm ([section 3.4](#)) under ITT population sorted by patient ID.

8.2 Site and Age

Counts and percentages of patients classified by age (< 65 and ≥ 65) at each site will be summarized using ITT population by treatment groups defined in [section 3.4](#). Denominator for site will be based on number of patients in ITT population for each treatment group and denominator for age classification will be based on number of patients within each site for each treatment group.

8.3 Medical /Surgical history

Medical history conditions, medical procedures will be coded using the Medical Dictionary for Regulatory Activities (MedDRA) version 23. Patients with any medical history, any ongoing medical history, any medical history resulting in concomitant medication, any medical history resulting in concomitant procedure will be summarized by counts and percentages by treatment arm. Patients with any medical history (SOC and PT) will be summarized using counts and percentages for the Safety population by treatment groups defined in [section 3.4](#). Medical history will be ordered by the highest frequency in the overall column by SOC and PT.

Medical history listings will be provided by treatment arm (grouping provided in [section 3.4](#)) sorted by patient ID for the Safety population, along with ongoing status of medical history and age/sex/baseline weight of the patient.

9. PRIOR AND CONCOMITANT MEDICATIONS & THERAPIES

Prior and concomitant medications and therapies will be coded using Anatomical Therapeutic Chemical (ATC) classification system version March 2020 which is controlled by the World Health Organization Drug Dictionary (WHO-DD). Medications will be mapped to the full WHO-DD Anatomical Therapeutic Chemical (ATC) class hierarchy, with ATC Level 2, ATC Level 4 presented as the primary interest for the analysis.

Concomitant medications and therapies are additional medications or therapies taken on or after the first dose of study treatment up and including the follow up period. Medications or therapies taken before first dose of study drug and stopped before the first dose of study drug will be classified as prior medication/therapy. If missing dates prevent a clear determination as to whether the medication or therapy is concomitant, the medication will be regarded as concomitant.

The number and percentage of patients using at least one prior or concomitant medication/therapy will be displayed together with the number and percentage of patients using at least one medication/therapy within each therapeutic class and preferred term. These will be summarized under Safety population for treatment groups defined in [section 3.4](#) and repeated for concomitant medication/therapy used for different purposes: adverse events, medical history or other.

Listing of full details of prior and concomitant medications/therapy (classification, medication taken, indication (adverse events, medical history or other), corresponding AE or medical history number, dosage, unit and route, start and stop dates/ongoing status will be provided by treatment arm (grouping provided in [section 3.4](#)) sorted by patient ID and visit for the Safety population, along with the age and sex and baseline weight of the patient.

10. TREATMENT EXPOSURE AND COMPLIANCE

SOC medications and therapies will be coded in the same manner as prior and concomitant medication/therapy with ATC Level 2, ATC Level 4 presented as the primary interest for the analysis. Summary of counts and percentages will be provided for all sites and for each site for the ITT, PPS and Safety population, with denominator being the available patients at each site.

- The Treatment Exposure (duration in days) is defined as:
Date of Last Study Drug Administration - Date of First Study Drug Administration + 1.

- The COVID-19 Treatment Exposure (duration) from randomization during the study is defined as:
Date and Last treatment - Date of Randomization + 1

- The overall COVID-19 Treatment Exposure (duration) during the study is defined as:

Date and Last treatment - Date of First COVID19 medication/treatment + 1 Both of these COVID-19 treatment exposure durations will be categorized into ≤ 15 days, > 15 days but ≤ 29 days, and > 29 days

- The Treatment Compliance is defined as:

For arm A: Total dosage taken / $(3 \times \{\text{Number of days in hospital up to 14 days}\}) \times 20$ mg=840mg)

For arm B: Total dosage taken / $(3 \times \{\text{Number of days in hospital up to 14 days}\}) \times 40$ mg=1680mg)

No treatment compliance is calculated for SOC as this differs between sites and regimen.

Treatment compliance with respect to counts and percentage of patients with $< 80\%$ and $\geq 80\%$ compliance will be reported.

- The Number of Days in Hospital (duration in days) is defined as:

Maximum of $\{\text{Date and Time of First Hospital Discharge} - \text{Date and Time of First Hospital Admission} + 1 \text{ or } 14 \text{ days}\}$.

Treatment exposure in duration and compliance will be summarized using descriptive statistics in accordance to [section 3.1](#) under ITT, PPS and Safety for treatment groups defined in [section 3.4](#). These information will be listed by Arm A and B sorted by patient ID and visit for the ITT and Safety population, along with the age, sex, baseline weight of the patient as well as the dates and times of study drug administration at each visit, whether the patient is in PPS, route and method of administration (after food, crushed) and whether drug administration was interrupted or missed and reasons for dose/study drug not administered.

For SOC, the listing will cover treatment exposure and will be sorted by patient ID and visit for the ITT and Safety population, along with the age, sex, baseline weight of the patient as well as site, ATC Level 2, ATC Level 4 classification of SOC medication/therapy, dosage, unit and route, start and stop dates/ongoing status.

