### 5.1 Inclusion Criteria

1. Male and female subjects aged  $\geq 18$  years of age
2. Confirmed coronavirus infection
  - a) Positive real-time fluorescence polymerase chain reaction of the patient's respiratory or blood specimens for SARS-CoV-2 nucleic acid
  - b) Viral gene sequences in respiratory or blood specimens that are highly homologous to SARS-CoV-2
  - c) Any other diagnostic test accepted by local regulatory authorities
3. Must be hospitalized and requiring supplemental oxygen, or on non-invasive ventilation or high flow oxygen devices (Score of 4 or 5 on WHO Ordinal Clinical Scale)
4. Female subjects of childbearing potential who are sexually active with a non-sterilized male partner must use at least 1 highly effective method of contraception (e.g. oral contraceptives, intrauterine device, diaphragm plus spermicide) from the time of screening and must agree to continue using such precautions for 90 days after the final dose of study drug(s)

5. Non-sterilized males who are sexually active with a female partner of childbearing potential must use condom plus spermicide from day 1 through 90 days after receipt of the last dose of study drug(s)
6. Subjects (or legal designate) must have the capacity to understand, sign and date a written, informed consent form and any required authorization prior to initiation of any study procedures

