### 6.2 Treatment Administration and Schedule

Tablet/s (20 mg TID arm = 1 tablet; 40 mg TID arm = 2 tablets) will be taken by mouth TID after food (if possible) in the in the morning (AM, upon rising), in the afternoon (PM, 6-10 hours following first dose), and evening (PM, 6-10 hours before the next day's anticipated first dose). Best efforts should be made to keep the three doses approximately 8 hours apart. The length of dosing for the study is up to 2 weeks (either to hospital discharge, or Day 14, whichever comes first).

The first dose of study medication will be taken on day 1 at the first visit, following randomization.

In cases where the patient is unable to swallow tablets the use of a nasogastric/stomach tube is permitted. Crushing and administration of tablets should follow local practices/SOPs.

Study drug administration should continue until the end of Day 14, or hospital discharge, whichever comes first.

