## 7.3 Visits

### 7.3.1 Visit 1 (Screening/Baseline/Enrollment)

At Visit 1, information will be collected for evaluation of trial eligibility by provided information as follows and patients will be randomized and dosed after confirmation of eligibility:

- Signing ICF (prior to any trial-related activities)
- Inclusion criteria and exclusion criteria
- Demographics (gender, date of birth, race and ethnic origin) and relevant medical and surgical history
- Confirmation of COVID-19 diagnosis (SARS-CoV-2 RNA confirmation). Include dates of onset of symptoms (if available) and initiation of treatment.
- Pregnancy test (females of reproductive age; Romania: Serum beta-human chorionic gonadotropin [ $\beta$ -HCG]; Rest of World: Serum beta-human chorionic gonadotropin [ $\beta$ -HCG] or urine test is acceptable)
- Vital signs measurements (including pulse, respiration rate, body temperature, systolic and diastolic blood pressure measured with the patient in a seated position [if possible] after  $\geq 3$  minutes of rest), and SpO2. Body weight and height will be included for the screening visit only
- Limited Physical Exam
- Assess baseline measures of clinical support
  - Hospitalized
  - Oxygen requirement
  - Non-invasive mechanical ventilation (via mask)
  - Mechanical ventilator requirement (via endotracheal tube or tracheostomy tube)
  - ECMO requirement
  - Ordinal Scale Assessment
    1. Not hospitalized, no limitations on activities
    2. Not hospitalized, limitation on activities
    3. Hospitalized, not requiring supplemental oxygen
    4. Hospitalized, requiring supplemental oxygen
    5. Hospitalized, on non-invasive ventilation or high flow oxygen devices
    6. Hospitalized, on invasive mechanical ventilation or ECMO
    7. Death
  - For the purposes of eligibility/baseline the worse score from the previous day (Day -1) will be used
  - NEW Score
- Safety laboratory testing
- Child-Pugh Score
- Cytokine Markers
- PaO2 and PaO2/FiO2 ratio
- ECG
- VAS (if possible)
- Extent of Dyspnea (if possible). For the first questionnaire (at baseline), the patient compares their current shortness of breath to their shortness of breath when they are well.)
- Concomitant medications documented
- Randomization\* after eligibility confirmation. All screening/baseline procedures must be completed prior to randomization and administration of study medication.

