Demographics/Medical History	•				
Physical Exam	•				
Vital signs ^c	•	•	•	•	
Clinical support data collection ^f	•	•	•	•	
Safety Laboratory Testing ^d	•	•	•	•	
Cytokine Markers ^k	•	•	•		
Child-Pugh Score ⁱ	•	•			
PaO2 and PaO2/FiO2 ratio ^j	•	•	•	•	
ECG	•				
Cough Severity (VAS) ^e	•	•	•	•	
Extent of Dyspnea (Likert Scale) ^e	•	•	•	•	
Adverse Events documented	•	•	•	•	•
Concomitant Medications	•	•	•	•	
Randomization	•				
Administer IP	•	•			
Vital Status					• ^g

^a Screening/baseline may occur up to 24 hours prior to randomization

^b Treatment can be given up to 14 days post randomization, or until hospital discharge, whichever comes first. If patient is discharged prior to Day 14, the next visit should be Visit 2.

^c Includes blood pressure (measured after the patient has been in a seated position (if possible) for ≥3 minutes of rest), pulse, respiratory rate, body temperature, and SpO2. Body weight and height will be measured at the screening visit only.

^d Baseline, Days 3, 5, 8, 11 if hospitalized, Day 15, Day 29

^e Baseline, Days 2, 4, 8, and 14 if hospitalized, Day 15 (if not done Day 14), Day 29

^f Includes NEW Score, on Baseline, Days 3, 5, 8, 11 if hospitalized, Day 15, Day 29

^g Vital status (is patient alive)

^h Baseline, Days 5 (or discharge, whichever comes first) and 15. Day 29 for patients with viral RNA detected at Day 15. Qualitative (mandatory) and Quantitative (if available) testing done all days.

ⁱ Baseline, Days 3, 5, 8, 11 if hospitalized

^j Minimum complete baseline, Days 3, 5, 8, 11, 15 and 29. If PaO2 not able to be taken, SpO2 should be obtained using a forehead sensor. Fingertip probes may be used if forehead sensors are not available. Remain consistent with the method of testing for the patient over the course of the study.

^k Cytokine markers at Baseline, Day 5, Day 15 (if available per local lab): IFN- γ , GM-CSF, IL-6, IL-12, TNF- α

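### SAP 10's compliance denominator, read literally, is 14 days for every patient, so a fully dosed patient discharged on Day 11 scores 33/42 = 79%

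*SAP*

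**What the plan says.** SAP 10 defines compliance as total dose taken divided by 3 x "Number of days in hospital up to 14 days" x 20 mg (arm A) or 40 mg (arm B). It prints 840 mg and 1680 mg as the values of those denominators.

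Lower in the same section, the number of days in hospital is the *Maximum* of two quantities: 14 days, and first discharge minus "Date and Time of First Hospital Admission" plus 1.

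On dosing, Protocol 6.2 gives the first dose on Day 1 after randomization and states: "Study drug administration should continue until the end of Day 14, or hospital discharge, whichever comes first". Footnote b to the schedule in SAP 2.1 agrees: "Treatment can be given up to 14 days post randomization, or until hospital discharge, whichever comes first".

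On reporting, the sentence in SAP 10 that begins "Treatment compliance with respect to counts and percentage of patients with" goes on to two classes, <80% and ≥80%. Compliance is summarised for the ITT, PPS and Safety populations. For the control arm: "No treatment compliance is calculated for SOC as this differs between sites and regimen".

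SAP 4.1.2 makes compliance with the investigational product one of the per-protocol criteria and gives no percentage. SAP 6 refers the categorisation of deviations that lead to PPS exclusion to a separate protocol deviation management plan.

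**The concern.** A compliance ratio should compare doses taken with doses due. Doses are due only until discharge or Day 14, so a patient who goes home early has a shorter course. The formula wording allows for that, but the operator *Maximum* and both printed totals do not. A programmer cannot satisfy all three.

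If the operator and the totals are followed, early discharge is scored as missed medication. The error has a direction: the sooner a correctly dosed patient leaves hospital, the lower the score. The <80% row would then mix patients who skipped doses with patients who recovered, and the summary table could not tell them apart.

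The start of the count is a second, separate fault. Days run from admission, before any study drug is due. Hospital days before randomization would count as undosed days wherever the 14-day figure does not already override the stay.

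**Working it through.** **Inputs.** Three doses a day, starting on Day 1 and ending at discharge or Day 14 (Protocol 6.2). Denominator wording, operator, printed totals and 80% cut from SAP 10. Assumption for the main calculation: three doses on every day from Day 1 to the discharge day d, so doses taken = 3d.

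**The plan's own figures.** 3 x 14 x 20 mg = 840 mg and 3 x 14 x 40 mg = 1680 mg. Both are exact, and both assume 14 days.

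**Literal rule.** The *Maximum* of the stay or 14 days is at least 14. With the formula's upper limit of 14 it is exactly 14 for everyone. The denominator is 3 x 14 = 42 doses and compliance is 3d/42.

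| Discharge day | Doses taken | Literal score | Score counted from first dose |
|---|---|---|---|
| 5 | 15 | 15/42 = 36% | 15/15 = 100% |
| 7 | 21 | 21/42 = 50% | 21/21 = 100% |
| 10 | 30 | 30/42 = 71% | 30/30 = 100% |
| 11 | 33 | 33/42 = 79% | 33/33 = 100% |
| 12 | 36 | 36/42 = 86% | 36/36 = 100% |
| 14 | 42 | 42/42 = 100% | 42/42 = 100% |

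In dose units, Day 11 is 660/840 mg in arm A and 1320/1680 mg in arm B. The 80% line is 0.8 x 42 = 33.6 doses, so Day 11 is the last discharge day below it. If Day 1 or the discharge day is partial and 31 or 32 doses are taken, the Day 11 score is 31/42 = 74% or 32/42 = 76%, still below 80%.

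If *Maximum* is applied without the upper limit, long stays fare worse. The Day 11 patient admitted 4 days before Day 1 scores 33/(3 x 15) = 73%.

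**Only the operator changed.** Suppose *Maximum* becomes *Minimum* and days still run from admission. With p hospital days before Day 1, compliance is d/min(14, d + p). The documents give no distribution for p, so a range is assumed.

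| Assumed p | Last discharge day below 80% | First discharge day at or above 80% |
|---|---|---|
| 1 | Day 3: 3/4 = 75% | Day 4: 4/5 = 80% |
| 2 | Day 7: 7/9 = 78% | Day 8: 8/10 = 80% |
| 3 or more | Day 11: 11/14 = 79% | Day 12: 12/14 = 86% |

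With 3 or more prior days the affected set is the same as under the literal rule. Both parts of the definition therefore need correcting.

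**Test of the simple repair.** Count whole days from first dose to discharge, and suppose only one dose was due on Day 1 and one on the discharge day. Doses taken = 3d - 4 and the score is (3d - 4)/3d. Day 6 gives 14/18 = 78% and Day 7 gives 17/21 = 81%. A patient who missed nothing can still fall below 80%, so the repair must also count only the doses due on the first and last days.

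**The case against.** The best defence is that a cap was intended. Both arm formulas limit the days to 14, a stay-dependent term would be pointless if every patient received 14 days, and the dosing rules stop at discharge. On that view *Maximum* is a slip for a ceiling, and 840 and 1680 mg are full-course values. The reading is plausible. But the operator and both printed totals contradict it, and nothing in the SAP says which governs. Even as a cap, the count from admission still marks down correctly dosed patients.

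It is also fair that the table is descriptive, that the SAP calls the pilot essentially exploratory, and that the same section summarises exposure from first to last dose and lists individual administrations. A reader could recover the truth from the listings, though not from the compliance summary.

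Three stronger readings are tempting, and the documents do not support them.

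- **That counting from admission produces the 79%.** Under the literal rule with its upper limit, the denominator is 14 days whatever the admission date. The admission start matters only once the operator is corrected.
- **That the per-protocol analysis is biased against ifenprodil.** Compliance is a per-protocol criterion and is not calculated for the control arm, so a reader might infer one-sided exclusions. But SAP 10 only reports the 80% split, and exclusions are categorised under a deviation plan that is not in the documents.
- **That every patient has at least one prior hospital day.** Protocol 7.3.1 says "For the purposes of eligibility/baseline the worse score from the previous day (Day -1) will be used", and Protocol 5.1 requires a "Score of 4 or 5 on WHO Ordinal Clinical Scale", which means hospitalized. But SAP 3.2 takes baseline on Day 1, and the schedule allows screening up to 24 hours before randomization. The number of prior days is therefore an assumption. Because SAP 10 subtracts dates and times, stays may also be fractional, and the whole-day cut-offs are approximate.

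**Conclusion.** The point holds as a self-contradictory definition that conflicts with the planned dosing period. It should be fixed before the compliance tables are programmed. Taken literally, SAP 10 places every patient who was dosed three times daily and discharged by Day 11 in the <80% row for ITT, PPS and Safety, with scores from 36% (Day 5) to 79% (Day 11). The admission start is a second fault, and its size depends on an assumed prior stay.

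The number of patients affected cannot be determined, because the documents give neither discharge timing nor length of prior stay. The sample-size table expects 36 + 37 = 73% of control patients to be out of hospital at Day 15. That suggests early discharge is not rare, but it is a Phase 3 planning assumption for Day 15, not a Day 11 figure.

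The demonstrated effect is confined to the descriptive compliance summaries. The ITT efficacy analysis does not use this measure.

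**What to change.** In SAP 10:

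1. Define expected dosing days as the minimum of 14 and (date of hospital discharge or death - date of first dose + 1). Death is needed because the present definition gives no end date for a patient who dies in hospital.
2. For patients randomized to ifenprodil but never dosed, use the randomization date in place of the first-dose date, so that they score 0%.
3. On the first day and on the day of discharge or death, count only the doses that were due, so that partial days are not scored as missed.
4. Set compliance = total dose taken / (expected doses x the assigned 20 or 40 mg).
5. Delete the printed 840 mg and 1680 mg, or label them as full 14-day values only.

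The cost is SAP wording and derivation code. No dose, visit or eligibility rule changes.
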